dyads reported benefits, the finding should be read considering a number of shortcomings such as the small sample, the intervention development at a single center and its delivery by a single nurse researcher.

It is therefore useful to contribute to the debate on the cachexia, so that we can develop reproducible and effective psycho-educational interventions.

Objectives of the Study

Primary objective: to evaluate the feasibility of a psycho-educational intervention on cachexia combined with a physiotherapy intervention on the cancer patient and his caregiver.

Secondary objective: improve the quality of life of patient and caregiver, acceptability of the intervention, adherence to each of the two psycho-educational and rehabilitative components.

What does this study contribute?

There are no studies on psycho-social interventions on dyads associated with rehabilitative interventions to support more functional relationships to the management of cachexia. The two psycho-educational and rehabilitative components have a strong rationale, common objectives and modalities with respect to the care of the patient and the family, compared with the multimodal approaches explored in the literature. We will evaluate the feasibility of the intervention in the population and context studied, estimating the effect of the intervention for a future multicenter efficacy study.

Methodology

Study design

Mixed methods study, non-pharmacological interventional perspective.

Sample and setting

Population of cancer patients with irreversible cachexia and their caregivers assisted by Palliative Care Unit, Azienda Usl - IRCSS of Reggio Emilia. The number of consecutive patients identified is 30.

Inclusion criteria

- Age of 18 years or older
- Good command of the Italian language
- Written informed consent
- Histologically confirmed tumor diagnosis
- Presence of irreversible cachexia and cachexia (ESPEN3-5 guidelines, MUST calculation)
- Patients who have identified a caregiver
- Patients and family members are informed of the diagnosis and the objectives of the therapies and who have reported awareness of the disease phase (evaluated by the palliative doctor).

Exclusion criteria

- Patients with prognosis less than three months to enable the rehabilitative intervention
- Presence of important mental disorder or dementia
- Severe sensory deficit
- Presence of diffuse bone metastases that put the patient at risk of fracture during rehabilitation exercise.

Intervention

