The intervention of psycho-education is in continuity with the other figures of the care team, which can be activated according to the needs that emerged (doctor, psychologist, nutritionist). The palliativist doctors will be informed of any information needs on the prognosis or on the clinical condition that may emerge during the psycho-educational intervention. If during the monitoring and supervision phase the need for a specialized psychotherapeutic course emerges, the psychologist of

the Psycho-Oncology Unit with skills in palliative care will be activated, particular attention will be given to patients with irreversible cachexia. Team meetings, which take place twice a week may be an additional space for sharing and discussion on the global management of the patients.

Rehabilitative intervention

The intervention is conducted by two trained physiotherapists and includes:

- 3 individual outpatient sessions (times T0, T1 and T2; see table), in which the physiotherapist, after evaluating the patient, sets up with him a program of personalized reinforcement exercises, which can be performed at home, even with the use of weights and / or elastic bands with different strength, if indicated.
- 3 home sessions of exercises per week; self-managed by the patient, or carried out with the help of the caregiver, for a total of at least 18 sessions in 6 weeks (24 in 8 weeks).

The contents of the intervention focus on:

- an educational component that stimulates patient self-management regarding physical activity, fatigue management, and goal-setting.
- The drafting of the personalized program of reinforcement exercises and the delivery of a booklet to help the patient perform the exercises at home, keeping a diary on the number of exercises, the duration, the number of repetitions and any critical issues that prevent completion of the defined program.
- Training for stretching and relaxation exercises, to be carried out at the end of each session.

Data collection strategies

Recruitment will last one year and all patients assisted by Palliative Care Unit will be evaluated during this period. Each patient will be offered both interventions (psycho-educational and rehabilitative) and will not be given the possibility to choose just one. All replies and reasons for any refusal to participate will therefore be kept.

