For each participant, basic information will be collected regarding: age, sex, marital status, family unit, education, profession, religious practice, location of the primary tumor, date of diagnosis, KPS, immediately after giving informed consent through these sources:

- direct request to the patient and / or caregiver
- UCP folder
- Matilde computerized file system.

Analysis

The evaluation will be carried out by trained operators who carry out their work outside the clinical area of the study and who will not have contact with the patients and families involved in the study in order to protect the data collection.

Primary objective: for the feasibility, the proportion of number of dyads who completed the intervention / involved dyads will be evaluated. Compliance will be assessed for each individual component (psycho-social and rehabilitative intervention). The overall intervention will be evaluated feasible if there is compliance greater than or equal to 50 percent to both interventions.

Secondary objectives:

The effects of the intervention will be evaluated on:

- quality of life and anorexia-cachexia syndrome related distress: Functional Assessment of Anorexia-Cachexia Therapy (FAACT)
- caregiver burden: Zarit Burden Scale

- family functioning in the palliative care setting: Family Functioning index
- physical performance Superior Arts: Hand-Grip strength test
- physical performance Lower Arts: 30 seconds sit-to stand test
- adherence to each of the two components (psycho-educational and rehabilitative) through participation in meetings and clinical diaries
- acceptability of the intervention through ad-hoc semi-structured interviews.

Measurement Scale

- Functional Assessment of Anorexia-Cachexia Therapy (FAACT)^{26,27}

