Evaluation scale composed by 12 items with a true / false answer, self-compiled, specifically used to evaluate family functioning in the palliative care setting. It is used as a screening tool to preventively assess families at risk of developing psychological distress associated with a disease with poor prognosis. It is based on the perception of family members and their level of cohesion, expression, and resolution of conflicts. The scale identifies five family types that are distributed along a continuum by families with good adaptation to the disease (supportive and able to face and resolve conflicts) to dysfunctional families with poor adaptation (hostile and silent, where a high index of anger is detected or latent). There is a defined intermediate family type that is placed between these types of family functioning (with good adaptation and poor adaptation).

In our study, the scale will be used to collect data useful for the evaluation of family functioning specifically associated with cachexia and the role of food in assistance (Do we talk about it in the family? Do we tend to avoid the subject? Is it possible to talk about the emotional problems related to cachexia? Is the problem faced or avoided). The scale will be self-completed separately by the patient, the caregiver (pre-intervention) and the nurse involved in the study during the psycho-educational intervention as support in the evaluation of the dyad interaction modalities.

There is a validated version in Italian³¹.

- Hand-Grip strength test³²

Test administered using a dynamometer, to quantitatively and objectively measure the isometric muscle strength of the patient's upper limbs. The best out of three attempts is accounted for. This test has been validated for patients with stroke outcomes, elderly and healthy adults. It has been used as a measure of physical performance in some studies with patients with oncological pathology, even at an advanced stage.

- 30 seconds sit-to stand test³³

It evaluates functionally the strength of the lower limbs. The test counts the number of times the patient can get up from a chair without arms within a period of 30 seconds. This test has been validated for patients with osteoarthritic and elderly problems. It has been used as a measure of physical performance in some studies with patients with oncological pathology, even at an advanced stage.

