- Ad-hoc semi-structured interviews aimed at the dyad one month after the intervention. The interviews will be conducted by a research nurse ([name]) trained in qualitative research and focus groups and by the PI of the study for a total of 7 interviews. The dyads will be chosen on the basis of pre and post intervention results, with particular attention to identifying the participants who have reported good adherence to the intervention and participants who have reported difficulties.

- Ad hoc semi-structured interviews with nurses and physiotherapists who participated in the study. The interviews will be conducted by the research nurse ([name]) and by the PI of the study for a total of 4 interviews corresponding to the operators involved (2 nurses and 2 physiotherapists).

Data analysis

The data analysis will be conducted by the Clinical and Statistical Studies Unit - IRCCS Reggio Emilia.

Sample size: since it is a pilot study to collect data on the feasibility of the intervention, the formal calculation is not carried out but is identified in 30 patients, according to criteria of opportunity and feasibility, the sample for the main objective. The statistical analysis will be descriptive: the primary endpoint will be represented with descriptive statistics tools (average, median, minimum, maximum, remarkable percentiles, central tendency index (with 95% CI), standard deviation, shape indexes.

secondary endpoints: descriptive representation (for T0, T1, T2 and T3) of the endpoints and of the variations detected between T0 and T3.

Ethical considerations

Access to clinical documentation

The researchers responsible for completing the Basic Information Sheet (Annex 11 Evaluation Scales) will collect only the data contained in the form (personal data and clinical data), by consulting the clinical documentation held by the Palliative Care Unit (Azienda USL - IRCCS of Reggio Emilia). The information collected will be limited to those contained in the form and aimed at carrying out psycho-educational and rehabilitative interventions. Please note that, to protect the privacy of all those involved:

- it is expected that the names of the dyad (patient / caregiver) will appear only in the aforementioned form, combined with a code
- in all the remaining forms, the patient will be identified exclusively with a code

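### A single-arm study promises an estimate of the intervention's effect, but its only change analysis is an uncontrolled T0–T3 difference

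*Combined protocol and SAP*

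**What the plan says.** The section *What does this study contribute?* commits the study to "estimating the effect of the intervention for a future multicenter efficacy study". The objectives use causal language as well: "Secondary objective: improve the quality of life of patient and caregiver". In *Analysis*, the list of secondary outcomes opens with "The effects of the intervention will be evaluated on" and then names FAACT, the Zarit scale, family functioning, hand-grip and the 30-second sit-to-stand test. Adherence and acceptability are in the same list but are not at issue here.

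On design, *Data collection strategies* says "Each patient will be offered both interventions (psycho-educational and rehabilitative) and will not be given the possibility to choose just one". No control group, randomisation, historical comparator or run-in period appears anywhere.

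On analysis, *Data analysis* says that all analysis is descriptive and gives one line to these outcomes: "secondary endpoints: descriptive representation (for T0, T1, T2 and T3) of the endpoints and of the variations detected between T0 and T3".

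The timetable of secondary outcomes places FAACT and Zarit at T0 and T3, the two physical tests at all four visits, and family functioning at T0 only. The description of the family scale under *Measurement Scale* agrees: patient and caregiver complete it before the intervention.

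**The concern.** A before-and-after difference in one group measures the intervention effect only if nothing else would have changed over the same eight weeks. In palliative patients with cachexia that is hard to assume. Disease course, repeat testing (grip and sit-to-stand are done four times), care from other professionals and selective loss before T3 all enter the difference.

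The direction of the error is unknown. Decline from disease would hide a benefit. Improvement from other care, or loss of the patients who are deteriorating, would look like one.

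The protocol's *Background* illustrates the problem. In the earlier before-and-after study of carers, weight-related distress fell in the control group as well as in the exposed group, and the protocol advises caution about that study partly because of its weak design. That study had a control group; this one does not.

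As written, the study may report a within-group change as an intervention effect and hand it to the planners of a multicentre trial.

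**Working it through.** **There is no planned figure to reproduce.** The sample of 30 is set on grounds of opportunity and feasibility, with no alpha, power, effect size or SD.

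**1. What the T0–T3 change estimates.** Expected change = intervention effect + change that would have occurred without it. The second term is given nowhere, so the first cannot be recovered. No other planned analysis could supply it: the physical tests at T1 and T2 also lack a comparator.

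**2. Illustration of the confounding (all inputs assumed).** Take a true effect of 0.5 SD and size a later two-arm trial on the observed change d, with one common SD, two-sided 5% and 80% power: n per arm = 2(1.960 + 0.842)²/d² ≈ 15.70/d².

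| Untreated change (SD) | Expected T0–T3 change (SD) | n per arm planned | n per arm needed |
|---|---|---|---|
| −0.5 | 0.0 | no finite size | 63 |
| −0.3 | 0.2 | 393 | 63 |
| 0 | 0.5 | 63 | 63 |
| +0.3 | 0.8 | 25 | 63 |
| +0.5 | 1.0 | 16 | 63 |

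**3. More patients do not help.** With the SD of change set to 1, the chance that the 95% CI of the change covers the true effect (noncentral t) is:
- untreated shift of 0.3 SD: 0.709 with 24 assessed, 0.645 with 30;
- untreated shift of 0.5 SD: 0.350 with 24 assessed, 0.246 with 30.

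Coverage falls as n rises because the error is bias, not imprecision.

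**4. Selective loss (p and d assumed).** Suppose a fraction p of patients alive at week 8 is not assessed, and their change would be d SD worse than that of those assessed. Overall mean = (1 − p) × mean of assessed + p × mean of missing, so the assessed mean is too favourable by p × d:
- p = 0.20: 0.20 × 0.5 = 0.10 SD, up to 0.20 × 1.0 = 0.20 SD;
- p = 0.40: 0.40 × 0.5 = 0.20 SD, up to 0.40 × 1.0 = 0.40 SD.

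**5. What the design can supply.** Sampling error is a separate matter from the bias, but it shows what the pilot can deliver. The 95% half-width of the mean change, in SD of change, is t(0.975, n − 1)/√n:
- n = 30: 2.045/5.477 = 0.373;
- n = 24 (if the 20% dropout quoted in *Background* applied here): 2.069/4.899 = 0.422;
- n = 18 (assumed 40% loss): 2.110/4.243 = 0.497.

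With 24 assessed, the true SD of change lies between √(23/38.08) = 0.78 and √(23/11.69) = 1.40 times its estimate. A loss of 6 out of 30 has a Clopper-Pearson 95% CI of 7.7% to 38.6%.

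**6. Family functioning.** *Analysis* lists it as an outcome on which effects are assessed. The timetable and the scale description give patient and caregiver one measurement, at T0. Even an uncontrolled change cannot be computed.

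**The case against.** The strongest reply is that the claim is a subordinate clause in a narrative section of a study titled and designed as a feasibility study. The primary objective is feasibility, the analysis is descriptive, no efficacy test or threshold is planned, and nowhere is the T0–T3 change named as the later trial's effect size. The verb in the secondary objective also governs acceptability and adherence, which suggests loose English. All of this is fair and limits the weight of the point. It does not remove it: *Analysis* repeats the effect wording, and no text restricts it to within-group change.

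Three narrower replies have some force.
- Referral to a doctor, psychologist or nutritionist is described as continuous with the psycho-educational work, so it may be partly the intervention as delivered. Granted, but disease course, repeat testing and selective loss remain.
- The exclusion "Patients with prognosis less than three months to enable the rehabilitative intervention" should limit deaths before an eight-week visit. It reduces loss but does not eliminate it, and prognosis is itself uncertain.
- Completion is counted in the primary endpoint and outcomes are described at each visit, so numbers assessed would normally be shown. The real gap is that nothing sets the T3 denominator, or a comparison of those with and without T3, beside the change.

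It is also true that the sampling-error figures do not size the defect; they show only what the pilot can offer.

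**Conclusion.** The concern holds. The plan claims an effect estimate that its design cannot produce, and it lists family functioning as an effect although no follow-up value is taken from patient or caregiver. The first conclusion rests on the absence of any comparator and on the single descriptive change analysis; the second rests on the timetable. Neither depends on the assumed numbers.

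The size of the confounding cannot be computed from the documents. The untreated shifts, the 0.5 SD effect, the loss fractions and the differences between assessed and missing patients are assumptions that show how far a later trial could be misled, in either direction. The primary feasibility endpoint is untouched. The change should be made, but the point does not undermine the study's main purpose.

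**What to change.** 1. In *What does this study contribute?*, and in *Analysis* for FAACT, Zarit, grip and sit-to-stand, replace the effect wording with: uncontrolled within-group change from T0 to T3, with its SD, within-person correlation and attrition (95% CIs), to plan a controlled trial. In the secondary objective, change the verb from improving to describing the T0–T3 change.
2. State that this change will not be used as the effect size of the future trial. If an effect estimate is wanted from this study, it needs a concurrent comparator.
3. List family functioning as a baseline descriptor.
4. Beside the T0–T3 change, report the number assessed, deaths and dropouts by visit, and the baseline values of those with and without a T3 assessment.

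Items 1 to 3 are wording, and item 4 is one extra table. No extra visits, forms or models are needed, though the protocol requires amendments to be authorised. The price is a more modest claim, and the later trial must justify its effect size from another source.

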- the data will be presented and published in aggregate form, without reporting information that can be traced back to the individual patient, the family caregiver, or the individual professional.

The study documentation will be collected and managed at one of the centers involved in the study (Palliative Care Unit, Azienda USL - IRCCS of Reggio Emilia). It will be kept and made available for any required inspections by regulatory authorities.

Consent to participation in the study

All study participants will be informed in detail by the investigator of the aims and objectives of the study, and must sign specific informed consent for the study and processing of personal data which will be filed together with the study documentation. The consent to participate in the study is requested and collected by the proposing doctor or by the researcher in charge of the T0 assessment. Each participant has the right to withdraw their membership in the study at any time.

The study will be conducted in accordance with this protocol, any amendments will be introduced and authorized and follow the ethical principles of the Helsinki Declaration.

Table time for the evaluation secondary outcomes.

Assessment	T0 (before intervention)	T1 (2 weeks after T0)	T2 (4 weeks after T0)	T3 (8 weeks after T0)
Functional Assessment of Anorexia-Cachexia Therapy (FAACT; patient)	x			x
Zarit Burden Interview (ZBI; caregiver)	x			x
Family Function Index (FFI; patient and caregiver)	x			
Hand-Grip (patient)	x	x	x	x
Sit-to-Stand (30CST; patient)	x	x	x	x
N sessions for rehabilitative intervention		x	x	x
N sessions for psycho-educational intervention			x	
Hoc semi-structured interviews (dyads)				x
Hoc semi-structured interviews (operators)				x

Bibliography

2. von Haehling S, Anker SD. Cachexia as a major underestimated and unmet medical need: facts and numbers. *J Cachexia Sarcopenia Muscle* 2010;1:1-5.

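### Family functioning is listed as an outcome for judging the intervention's effect but is measured only at T0, so no change can be computed for any dyad

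*Combined protocol and SAP*

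**What the plan says.** Five places in the combined protocol and SAP bear on this.

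- **Analysis, Secondary objectives.** The list opens with "The effects of the intervention will be evaluated on" and includes "family functioning in the palliative care setting: Family Functioning index".
- **Data analysis.** The plan is "secondary endpoints: descriptive representation (for T0, T1, T2 and T3) of the endpoints and of the variations detected between T0 and T3". No outcome is excepted.
- **Measurement Scale, Family Relationship Index.** "The scale will be self-completed separately by the patient, the caregiver (pre-intervention) and the nurse involved in the study during the psycho-educational intervention". The nurse's use is described as an aid to judging how the dyad interacts.
- **Psycho-educational intervention.** The nurse uses the family-functioning tool at the first meeting to draw an initial picture of the dyad.
- **Table of times for the secondary outcomes.** The row beginning "Family Function Index (FFI; patient and caregiver" has one mark, in the column whose heading begins "T0 (before intervention". Its T1, T2 and T3 cells are empty.

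The scale has three names: Family Functioning index in the outcome list, Family Relationship Index in the description, and Family Function Index in the table. I read them as one instrument, since no other family scale is described.

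**The concern.** An effect in an uncontrolled study can only be described as a change from before to after. Here the before value is planned and the after value is not. The outcome list and the analysis text therefore promise something the schedule cannot deliver.

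The outcome is close to the study's rationale. The protocol presents its novelty as combining dyad-based psychosocial support with rehabilitation so that relationships around cachexia work better, and the psycho-educational meetings aim to strengthen how the dyad copes. It also intends to estimate effects to inform a later multicentre efficacy trial. For family functioning, that later trial would inherit a baseline distribution only: no change, no variability of change, and no T3 completion rate.

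**Working it through.** No power or sample-size figure is involved and there is no stated result to reproduce: the 30 patients were chosen on grounds of opportunity and feasibility, and the analysis is descriptive. The check compares the schedule with what the analysis needs.

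**Step 1. What the analysis needs.** For each person, change = score at T3 − score at T0. Both scores must come from the same rater on the same scale.

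**Step 2. What the table schedules.**

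| Scale or test | T0 | T1 | T2 | T3 | T0–T3 change possible? |
|---|---|---|---|---|---|
| FAACT (patient) | x | | | x | yes |
| Zarit (caregiver) | x | | | x | yes |
| Family index (patient and caregiver) | x | | | | **no** |
| Hand-grip (patient) | x | x | x | x | yes |
| Sit-to-stand (patient) | x | x | x | x | yes |

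Of the five scales and tests, only the family index has no measurement after T0.

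**Step 3. Could this be a table error?** The scale's description separately places patient and caregiver completion before the intervention. Two independent places agree, so a mark lost from the table is not a likely explanation.

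**Step 4. Count the pairs.** The planned sample is 30 patients, and the inclusion criteria require each to have an identified caregiver, which I take as one per patient. Planned T0 forms: 30 + 30 = 60. Planned T3 forms: 0. Usable T0–T3 pairs: 0 of 30 patients and 0 of 30 caregivers.

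**Step 5. Could another source supply the effect?**

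- *Control group.* None is described, and every patient is offered both components, so no between-group contrast exists.
- *The nurse's ratings.* These come from a different rater, during delivery, to support the meetings, and they are not in the assessment table. They give no post-intervention patient or caregiver score.
- *Zarit.* It is measured at T0 and T3 and touches the caregiver–patient relationship, but as one area within a burden score and from the caregiver only.
- *Interviews.* The outcome list assigns them to acceptability. Only 7 dyad interviews are planned, with dyads chosen purposively.

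None of these gives a change in family functioning.

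**The case against.** The strongest reply is that the index was never meant as an effect outcome. Its description calls it a screening tool for families at risk, the nurse uses it for a first assessment, and the table puts it at T0; these three places agree with each other. On that reading the fault lies in the general lead-in to the outcome list. That lead-in cannot be fully literal anyway, since the same list contains adherence and acceptability, which are not effects and have no baseline. Nor can the sentence in Data analysis apply to every endpoint at every time point, because FAACT and Zarit are not scheduled at T1 or T2. Family functioning is also absent from the secondary objectives stated earlier in the protocol, which are quality of life, acceptability and adherence.

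Much of this stands. The screening reading is plausible, no formally stated objective goes unanswered, and the documents say nothing on whether the index is sensitive to change over 8 weeks. But the reply moves the error rather than removing it: if the index is a baseline descriptor, the outcome list is wrong and must be edited. The comparison with adherence and acceptability does not help either. Those are process measures that can only exist once the intervention is under way, whereas family functioning has a baseline and no follow-up.

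**Conclusion.** The concern holds. As written, the plan lists family functioning for effect evaluation and schedules no measurement from which an effect or a T0–T3 change could be computed, for any of the 30 dyads. This rests on the three names denoting one instrument, on one caregiver per patient, and on there being no comparison group; the documents support each of these.

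The consequence is limited in scope. The endpoint is secondary and descriptive, and the feasibility criterion of at least 50 percent compliance with both components is untouched. It still warrants correction before enrolment, because a T3 score that was not collected cannot be recovered by later analysis.

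**What to change.** Choose one of two, according to what the sponsor intends.

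1. **If change is wanted:** mark the family index at T3 for patient and caregiver in the table. In the scale description, replace the pre-intervention timing with T0 and T3 rather than simply deleting it, so that the timing remains stated. State that the nurse's ratings are for delivery of the intervention and are not outcome data. The cost is one table row and one line of text, plus at most 30 + 30 = 60 extra forms of 12 true/false items, at a visit where the patient already completes FAACT and the caregiver Zarit. The documents give no completion time; I assume a few minutes per person. The result would still be an uncontrolled before–after change and should be reported as such.
2. **If only a baseline descriptor is wanted:** remove family functioning from the list of effects, report it with the T0 characteristics, and except it from the T0–T3 variation in Data analysis. This is wording only, and it fits the current table and scale description.

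In either case, use one name for the instrument throughout.

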Evaluation scale for anorexia-cachexia related distress. It is a tool that derives from the Functional Assessment of Cancer Therapy-General (FACT-G), includes several sub-scales, developed and validated to measure the quality of life related to health status, in particular in cancer patients undergoing therapy: wellness physical, social / family well-being, emotional well-being and functional well-being. To these 4 sub-scales, which contain a total of 28 items, 12 specific items were added on problems related to the presence of anorexia-cachexia. Each item can be assigned a score ranging from 0 'Not at all' to 4 'Very much'; higher scores indicating greater quality of life. The questionnaire can be self-completed or administered by a trained person.

In our study we will use only the sub-scale related to anorexia-cachexia self-compiled by the patient²⁷.

- Zarit burden scale²⁸⁻³⁰

The Zarit Burden Interview (ZBI) is a 22-item instrument for measuring the caregiver's perceived burden of providing family care. The 22 items are assessed on a 5-point Likert scale, ranging from 0 = 'never' to 4 = 'nearly always'. Item scores are added up to give a total score ranging from 0 to 88, with higher scores indicating greater burden. The questions focus on major areas such as caregiver's health, psychological well-being, finances, social life and the relationship between the caregiver and the patient.

This scale has been widely used for many years, has been translated into 18 languages²⁹, Italian validation is available³⁰.

In our study it will be self-compiled by the caregiver.

- Family Relationship Index³¹

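### Does the FAACT anorexia-cachexia sub-scale lack a usable score direction and scoring rule?

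*Combined protocol and SAP*

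**What the plan says.** In the Analysis section, the list of secondary outcomes assigns one instrument to two constructs: "quality of life and anorexia-cachexia syndrome related distress: Functional Assessment of Anorexia-Cachexia Therapy (FAACT".

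The FAACT entry under Measurement Scale opens with "Evaluation scale for anorexia-cachexia related distress". It explains that "12 specific items were added on problems related to the presence of anorexia-cachexia", and then gives the anchors and the direction: "Each item can be assigned a score ranging from 0 'Not at all' to 4 'Very much'; higher scores indicating greater quality of life". It ends with "In our study we will use only the sub-scale related to anorexia-cachexia self-compiled by the patient". References 26 and 27 are cited at the heading of the entry, and 27 again on the sentence that selects the sub-scale. The entry gives no list of reversed items, summing rule, sub-scale range or missing-item rule.

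The next entry, for the Zarit Burden Interview (ZBI), is fuller: "Item scores are added up to give a total score ranging from 0 to 88, with higher scores indicating greater burden".

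The timing table at the end of the protocol schedules the FAACT at T0 and T3 only. Data analysis plans "descriptive representation (for T0, T1, T2 and T3) of the endpoints and of the variations detected between T0 and T3" for the secondary endpoints.

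**The concern.** Taken word by word, the FAACT entry seems to conflict with itself. A patient who has every listed problem to the greatest degree would give the top answer to each item and so get the highest score, while the text says high scores are good. The label of a distress scale adds to the impression that the score could run either way. The contrast with the ZBI entry makes the silence on reversal and summing more noticeable.

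The sub-scale is the only patient-reported scale scheduled at both T0 and T3, so the patient part of the quality-of-life objective rests on it. The section on the study's contribution wants effect estimates for a later multicenter trial, and a change with the wrong sign would mislead that work. The results might also feed into the choice of seven dyads for interview, since "The dyads will be chosen on the basis of pre and post intervention results".

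**Working it through.** **Inputs.** From Measurement Scale: 12 sub-scale items, each scored 0 to 4, higher stated to be better; ZBI 22 items, each 0 to 4, total 0 to 88. From Data analysis: 30 patients, no formal calculation. The plan gives no FAACT total, so there is no FAACT figure to reproduce. Assumptions: a plain sum, and k problem-worded items, because the item wording is not in the documents.

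**Check of the method on the ZBI.** 22 × 4 = 88, which matches the stated maximum.

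**Sub-scale range.** 12 × 4 = 48, so 0 to 48.

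**What an unreversed score would do.** Let every item improve by one category. Keyed correctly, the change is 12 × 1 = +12. With k problem-worded items left unreversed it is (12 - k) - k = 12 - 2k. The best possible state then scores 4(12 - k) and the worst 4k.

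| k | Change shown | Best state | Worst state |
|---|---|---|---|
| 0 | +12 | 48 | 0 |
| 3 | +6 | 36 | 12 |
| 6 | 0 | 24 | 24 |
| 7 | -2 | 20 | 28 |
| 9 | -6 | 12 | 36 |
| 12 | -12 | 0 | 48 |

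**Does the plan permit these rows?** The direction is given in the same sentence as the item scores. Applied to each item, it excludes every row with k above 0, because a problem item left unreversed runs the wrong way. Applied only to the total, it still excludes k = 6 and above, where the best state no longer scores higher than the worst. The text describes all the added items as concerning problems, which is the k = 12 row and the one that most plainly contradicts the stated direction. An analyst who accepts the sentence has to reverse.

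**Missing items.** Take an unchanged patient with an item mean of 2, so the T0 sum is 24. With 1, 2 or 3 blanks at T3 counted as zero, the sum is 22, 20 or 18 and the change is -2, -4 or -6. Prorated, 22 × 12/11 = 20 × 12/10 = 18 × 12/9 = 24, a change of 0. With an item mean of 1 the counted-as-zero changes are -1 to -3; with 3 they are -3 to -9. Nothing in the plan suggests counting blanks as zero. The ZBI entry has no missing-item rule either, so this silence is not peculiar to the FAACT.

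**Interview selection.** Seven of 30 dyads is 7/30 = 23%, if 30 are enrolled. The selection sentence goes on to stress good adherence and reported difficulties. No section ranks dyads by FAACT change, and the ZBI, grip strength and sit-to-stand results are also measured before and after.

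**Objective wording.** Objectives of the Study mentions quality of life for the caregiver as well as the patient. The list of secondary outcomes in Analysis settles what is measured for the caregiver: burden, by the ZBI.

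**The case for a change.** The best case for a change is that it would cost one sentence and no patient burden. The authors wrote out the ZBI scoring in full, so the omission for the FAACT is not house style. The sentence selecting the sub-scale cites only reference 27, which the Bibliography lists as a piece on quality of life and nutrition. It does not cite reference 26, the re-validation paper for this questionnaire. Annex 11 is mentioned in connection with the basic information sheet and not for scoring. Blanks are plausible on a self-completed form in palliative care.

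The facts in this stand: the visible text does not restate reversal, summing, range or handling of blanks. Whether the references or the annex supply them cannot be checked here. What does not follow is that the endpoint has no direction or two directions. Reference 26 is cited at the head of the same entry, so the instrument is tied to its published source. Naming that source again would be tidy, but it would not alter the score of an analyst who already follows the stated direction.

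**Conclusion.** The concern does not call for a change. The plan states one direction, and for problem-worded items that direction already implies reversal. The rest is scoring detail of a named, referenced questionnaire, which the institute's statistics unit can be expected to take from its source and apply in the same way at T0 and T3. The possible swing from +12 to -12, and the losses of 2 to 6 points from blanks at an item mean of 2, measure mistakes that the plan neither prescribes nor suggests.

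The reach is also small: one secondary outcome, reported descriptively, in a pilot of 30 patients. The criterion of at least 50% compliance with both interventions and the sample size do not involve the FAACT.

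This conclusion rests on two assumptions: that the cited sources or the annex contain workable scoring instructions, and that the analysts follow the stated direction. Some freedom remains over blanks, chiefly whether to prorate or to leave the score missing. That choice can be reported with the results.
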